
Exclusion Criteria
	
5) Note: IF UP/Cr less than 2000 mg/gm, a formal 24-hour urine collection for total protein can be performed. The total 24-hour protein will need to >= 2000mg.
 
6) Blood pressure targeted to \leq 140/90 at the time of randomization
 
7) Patients with MGUS without history of myeloma WILL be eligible.
 
8) Patients with monoclonal staining for fibrillary fibers will be excluded
 
9) Patients with Type II non-insulin dependent diabetes WILL be eligible provided the renal biopsy does not show nodular Kimmelstiel Wilson lesions
 
Exclusion Criteria;
 
1) Patients with MGUS and history of myeloma WILL NOT be eligible
 
2) Patients with active viral production of either hepatitis B or C as evidence by historical PCR test positive for active viral shedding
 
3) HIV seropositivity
 
4) Renal biopsy data with > 50% Interstitial Fibrosis
 
5) Patient with active or a known history lymphoma
 
6) Patients with insulin Dependent diabetes mellitus will be excluded
 
Note: patients with Type II diabetes mellitus that are well controlled WITHOUT the need for insulin WILL be eligible for the study.
 
7) Patients with Type II non-insulin dependent diabetes WILL be eligible provided the renal biopsy does not show nodular Kimmelstiel Wilson lesions.
 
8) Patients receiving steroids, MMF, cyclophosphamide, Azathioprine or other immunosuppressive agent with 4 weeks of study randomization Note: Washout of these medications will be allowed at the screening visit
 
9) Patients having received Rituximab or B cell modifying biologic therapy within 6 months of randomization

----------------------------------	---

Primary Endpoint:	Primary Endpoint: The change in UP/Cr ratio in patients with biopsy proven Fibrillary GN after 12 months of treatment with treated with ACTHar gel (80 units SQ 2X/week) alone OR in combination with oral Tacrolimus (1.0 mg PO BID). The change in UP/Cr for each group will also be compared to baseline UP/Cr ratios prior to randomization

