
Number of total Clinic Visits
 
FACT-Trial: Study Design
	
conference call with the prospective patient will be arranged to discuss in details of the study; the risks/benefits of the study drug, as well as details regarding patient requirements and travel to and from the study site. The patient will be given time to review the consent with their families and other physicians.
 
If is determined by the Medical Director and the FACT Site PI that the patient is a likely candidate for the study, a travel agent will contact patient and make arrangements for airfare and overnight accommodations to visit the FACT PI. Both the airfare and overnight accommodations will be provided by NephroNet. If a patient lives within approximately 4 hours of the FACT site, they will be reimbursed for mileage and hotel. There will be a total of 13 visits per patient per site.
 
Patients agreeing to participate in the FACT sign consent at their first screening visit.
 
Thirteen (13) visits for total study: Pre-screening visits- two (2) Study Drug Treatment visits- six (6) Post Study Drug Treatment visits- five (5)
 
Study Design: This study will be a multi-center, prospective, randomized, open-labeled intervention trial of 34 patients randomized to 52 weeks of ACTHar gel alone or ACTHar gel plus oral Tacrolimus.
 
Drug Dosing:
 
Group-1: ACTHar gel alone-patients will be receive 80 units SQ Q 2X/week for 52 weeks
 
Group-2: ACTH gel 80 units 2X per week plus oral Tacrolimus (1.0 mg BID) titrating to a trough level of 4-6 ng/ml for 52 weeks
 
Note: Patient with type II diabetes will be allowed to dose at 24 units/day (0.3 mls SQ Q day) to reduce glucose fluctuations and simplify management of diabetes at the discretion of the PI.
 
Protocol-Schedule and Follow Up: Clinic Visits:

---	--

- **Visit 1: Pre-Randomization Screening & Consenting Visit:** Patients that have gone through the Pre-screening review and considered to be eligible for study participation will be seen by the local site PI for formal consenting two months prior to study randomization. The patient will then be seen by the FACT trial site PI who will perform a complete physical exam and obtain routine laboratory testing including a urine to protein Cr ratio.

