Pre-Randomization Screening & Consenting Visit (V1): Blood and Urine Study Samples: Blood samples (5 mls) for serum and plasma will be obtained at each visit. Blood samples will be centrifuged at 3000 RPM for 5 minutes and 250 ul of plasma or serum will be transferred to an O-ring sealed cryovials and frozen at -80°C until analyzed. Each 10-ml sample of urine will be added to 100 ul of Thermo Scientific HALT proteinase inhibitor solution and then centrifuged at 3,000 rpm for 10 minutes at 4°C. Then, 250 µL of the urine supernatant will be transferred to an O-ring sealed cryovials and frozen at -80°C until analyzed.

- **Visit 2: Pre-Randomization Screening #2) "Optimization & Run-In Phase":** After the initial pre-screening visit, the prospective patients will enter a 4-week "optimization and run-in phase" during which patients will have their blood pressure optimized to a "pre-randomization" target level of 140/90. During the "run-in phase", RAAS blockers will not be modified and target blood pressure will be achieved using antihypertensive agents that do not alter urinary protein excretion (e.g. Nifedipine, Hydralazine).
- **Visit 3: Randomization/Baseline:** After the 4-week run-in phase, patient will be flown back to the FACT trial site where they will undergo formal randomization. When the site PI determines that the patient has met all inclusion and exclusion criteria, they contact [name] and the NephroNet data coordinating center for randomization. Each patient will then undergo a physical exam and routine blood and urine laboratory studies. The UP/Cr from the pre-

screening and randomization visits will be averaged and this value will be considered the “baseline UP/Cr” for that patient.

Note: If the pre-screen and randomization UP/Cr values differ by more than 50%, the patient will be allowed to collect a third UP/Cr ratio one week later. The average of those 3 UP/Cr ratios will be recorded as the patient’s baseline proteinuria.

Baseline- Blood and Urine Study Samples: Blood samples (5 mls) for serum and plasma will be obtained at each visit. Blood samples will be centrifuged at 3000 RPM for 5 minutes and 250 ul of plasma or serum will be transferred to an O-ring sealed cryovials and frozen at -80°C until analyzed. A 10-ml sample of urine will be centrifuged at 3,000 rpm for 10 minutes at 4°C. Then, 250 µL of the supernatant will be transferred to an O-ring sealed cryovials and frozen at -80°C until analyzed

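### AE/SAE recording is scheduled only from randomisation (V3), so events from the immunosuppressant washout and blood-pressure run-in that follow consent at V1 are not recorded as AEs or SAEs when they occur

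*Protocol*

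**What the plan says.** Four places in the protocol bear on this.

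- **Consent.** Under Visit 1, a patient who has passed the records review "will be seen by the local site PI for formal consenting two months prior to study randomization". The text on clinic visits agrees: "Patients agreeing to participate in the FACT sign consent at their first screening visit". The schedule marks informed consent in the V1 column, at -2 months.
- **Washout.** Exclusion criterion 8 bars steroids, MMF, cyclophosphamide, azathioprine and other immunosuppressants in the 4 weeks before randomisation, then adds: "Note: Washout of these medications will be allowed at the screening visit".
- **Run-in.** Under Visit 2, RAAS blockers stay fixed for 4 weeks and "target blood pressure will be achieved using antihypertensive agents that do not alter urinary protein excretion". Randomisation comes afterwards: "After the 4-week run-in phase, patient will be flown back to the FACT trial site where they will undergo formal randomization".
- **AE/SAE collection.** The AE/SAE row of the schedule is empty at Pre-Screen, V1 and V2. It is marked at V3 and in every later column through V13.

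The Statistical Analysis paragraph compares AE frequencies by Fisher's exact test. It limits the intention-to-treat analysis to patients with at least a week on study drug.

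**The concern.** Stopping immunosuppression to meet an eligibility rule, and adding or changing antihypertensives to reach a protocol target, are interventions made because of the trial in people who have already consented. They can cause harm, such as a disease flare, a steroid-withdrawal event or hypotension. The schedule does not call for such events to be recorded as AEs or SAEs in the weeks when they would occur.

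Two things are at stake. The first is oversight: those responsible for safety would not see harm from the screening procedures, least of all in patients who drop out before randomisation. The second is the description of harm in each arm. The first AE/SAE mark and the first study-drug mark both fall at V3. A problem that began in washout, such as worsening edema or a falling eGFR, and is first entered at V3 or later can therefore pass as having started on treatment.

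**Working it through.** No sample-size or power figure is involved. The check reads the schedule row by row and then sets it against the visit text.

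**Step 1. First mark in each relevant row** (ten columns: Pre-Screen, V1, V2, V3, V4, V5-7, V8, V9, V10-12, V13):

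| Row | Columns marked |
|---|---|
| Informed consent | V1 |
| Full H&P | V1, V3, V8, V13 |
| Limited H&P | V2, V4, V5-7, V8, V9, V10-12 |
| Blood pressure | V1 and every later column |
| CMP | V1, V2, V3, V5-7, V8, V10-12, V13 |
| AE/SAE | V3 and every later column (7 marks) |

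The seven AE/SAE marks fit the seven columns V3 to V13 exactly, while the blood-pressure and CMP rows do carry marks at V1 and V2. The blanks are therefore unlikely to be an effect of how the table was read.

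**Step 2. Length of the uncovered interval.**

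- Consent to first AE/SAE mark: V1 at -2 months to V3, about two months, with visit windows of +/- 2 weeks.
- Washout: at most about two months, if drugs are stopped at V1. At least about 4 weeks, because criterion 8 requires the patient to be off them that long before randomisation.
- Run-in: all 4 weeks. The V2 column places it from about -1 month. The Visit 2 text has it follow the initial pre-screening visit, which could be earlier. On either dating it ends at V3 and lies wholly outside AE/SAE collection.

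**Step 3. Who is missed.**

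- *Consented, never randomised.* There is no V3, hence no AE/SAE mark at all, and no place in the analysis set, which requires study drug.
- *Randomised.* V1 to V3 include an H&P, blood pressure and CMP, so some events may show up clinically, and the AE/SAE entry at V3 may look back. The protocol states no look-back period and does not distinguish onset before first dose from later onset.

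**Step 4. Effect on the AE comparison.** Washout and run-in precede randomisation, so pre-dose events are expected equally in both arms. Counting them as on-treatment raises each arm's rate without favouring either. For scale, one patient so counted moves an arm's rate by 1/17 = 5.9 percentage points. That is the weight of one patient in an arm of 17, not an estimate of how often this would happen.

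**The case against.** The strongest reply is that little is lost for randomised patients. AE/SAE is assessed at V3, where an ordinary enquiry would cover the preceding weeks, and three visits up to V3 give examinations and laboratory values that can show prior onset. Starting AE collection at randomisation is a choice that no other text contradicts, and the definition of treatment-emergent events can be left to a SAP. Part of the text at hand also breaks off between the secondary endpoints and the visit description. The abbreviation list includes terms, such as AESI and a safety review committee, that the visible text never uses, so a fuller safety section cannot be ruled out.

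Much of this stands, and it narrows the point. A reader might infer that all harm before V3 goes unseen; the scheduled examinations and tests do not support that. A reader might infer that the Fisher comparison is biased; because both arms share the period, the documents support only added noise. A reader might multiply 34 patients by 2 months and call the resulting 68 patient-months unmonitored exposure to trial interventions. But washout is only permitted, for patients still taking such drugs, and someone already at the blood-pressure target may need no change. Nor does the Background's biopsy series show that washout will be common: it reports earlier treatment, not treatment current at screening.

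What the reply does not remove is the gap for screen failures, and for events that resolve or go unnoticed before V3. When collection starts is fixed by this protocol's schedule; it is not a detail left to a SAP.

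**Conclusion.** The point holds in a limited form. As written, events caused by washout or run-in changes are not scheduled for AE/SAE recording at V1 or V2. A patient harmed in that period who is never randomised may appear in no AE/SAE data. The gap is about two months from consent, including the full 4-week run-in and at least about 4 weeks of any washout. The numbers of screen failures, washed-out patients and affected events cannot be derived from the protocol.

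The main harm is to safety oversight and to each arm's absolute AE profile; the between-arm test is touched only by noise. The conclusion assumes that the schedule governs when recording starts and that no safety section outside the text at hand begins it at consent. If such a section exists, the schedule should be brought into line with it. This is an inexpensive improvement to safety reporting, not a threat to the primary endpoint.

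**What to change.** - In the schedule of assessments, mark AE/SAE at V1 (after consent) and at V2.
- State that SAEs, and AEs related to washout or run-in changes, are recorded from signature of consent, including in patients who fail screening.
- Record an onset date for every event, and report events that began before first dose separately from treatment-emergent ones.

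The cost is two schedule cells, an onset date or pre-treatment flag in the eCRF, and a few more AE entries. Both visits already take place with an H&P, blood pressure and laboratory tests. No dose, eligibility rule or clinical management changes.

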Hypothesis and Specific Aims	
Hypothesis#1: A 12-month treatment with combination ACTHar gel and Tacrolimus therapy will be superior to ACTHar gel therapy alone in lowering urinary protein to creatinine (UP/Cr) ratios in patients with idiopathic DNA-JB9 positive Fibrillary GN
 
Specific Aim #1-will randomize 35 patients with biopsy proven DNA-JB9 positive Fibrillary glomerulopathy to receive a 12-month course of ACTHar gel at 80 units SQ 2X/week alone or in combination with oral Tacrolimus at 1.0 mg BID (targeting for trough Tacrolimus dose of 4-6 ng/ml).
 
Hypothesis#2: Treatment with combination ACTHar gel and Tacrolimus therapy will result in a higher eGFR after 24 months of follow up than patients randomized to ACTHar gel therapy alone
 
Specific Aim #2-will determine the change in eGFR from baseline to 24 months of follow for patients with biopsy proven DNA-JB9 positive Fibrillary glomerulopathy. It is anticipated that at 24 months (12 months after completing therapy) patients randomized to ACTHar gel plus Tacrolimus will have higher eGFR compared to patients receiving ACTHar gel alone.
 
Hypothesis #3: Combination therapy of ACTHar Gel and Tacrolimus in patients with DNA-JB9 positive Fibrillary Glomerulopathy will lead to significantly lower urinary markers of podocyte injury compared to patients receiving ACTHar gel therapy alone.
 
Specific Aim #3-will compare the relative changes in the following urinary biomarkers will be performed:
 
1. Urinary VEGF 121, VEGF-1652. Urinary VEGF-189, VEGF-2063. Urinary MCP-14. Urinary Synaptopodin5. Urinary TGF-beta6. Urinary Podocalyxin7. Urinary Nephryn 
Levels will be measured at baseline prior to treatment and after 12 months of ACTHar ge therapyl alone or in combination with oral Tacrolimus. The relative reduction urinary biomarkers will also be compared between the two treatment groups.

Study Population	
A total of 34 patients will be enrolled.
 
Group 1 (17 patients) ACTHar gel 80 units 2X/week alone for 12 months of therapy.
 
Group 2 (17 patients) ACTHar gel 80 units 2X/week plus oral Tacrolimus 1.0 mg BID titrated to trough Tacrolimus levels between 4-6 ng/ml
 
Anticipated drop out rate 10%.

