Secondary Endpoint	Secondary Endpoints: 
1) The relative change in UP/Cr at 24 months (12 months after stopping both ACTH and Tacrolimus) in the ACTHar gel group and the ACTHar gel + Tacrolimus group.2) The percentage of patients in the ACTHar gel alone versus ACTHar gel + Tacrolimus group that achieves complete, partial or clinical responses after 12 months of therapy3) The change in eGFR (measured by CKD-EPI formula) between the ACTHar gel and ACTHar Gel + Tacrolimus groups after 24 months of treatment with ACTHar gel alone or in combination with oral Tacrolimus. In addition, we will also compare the relative change in eGFR between those patients receiving ACTHar gel alone with those randomized to combination therapy.4) To compare the change in urinary biomarkers (see below) at baseline and after 12 months of treatment with ACTHar gel alone or in combination with Tacrolimus. The patients urinary biomarker levels after 12 months of therapy will be compared between the ACTHar gel alone group and ACTHar gel + Tacrolimus group.
a) Urinary VEGF 121, 165 189, and206b) Urinary MCP-1c) Urinary Synaptopodind) Urinary TGF-betae) Urinary Podocalyxinf) Urinary Nephryn 
Fibrillary GN patients with concurrent Type II diabetes mellitus: To determine whether ACTHar gel therapy resulted in

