- **Visit 4: 14 Days Post Randomization Visit:** 14 Days Post Randomization (Visit 4) will be optional for patients traveling from long distances. Would request that patient visit nephrologist in home town if any adverse events of concern are reported.
- **Visits 5 – 7: Study Visits-Months 3 (V5), 6(V6) & 9(V7) :** We will be conducted in like manner to Randomization visit. Each patient will get a complete physical exam. Standard blood and urine studies will be performed as well as plasma, serum and urine study sample collections. Tacrolimus Trough Levels will be drawn for those patients randomized to the Tacrolimus arm.
- **Visit 8: Month 12: Primary Endpoint Evaluation:** All patients completing of 52 weeks of ACTHar gel therapy alone or in combination with Tacrolimus will be examined for their change in UP/Cr as compared to their baseline levels of urinary protein. Patients will be asked to bring 2 first morning voids of urine. These two samples will be averaged and used for

determination of the percentage of patients achieving the primary endpoint.

Complete Responders: < 300 mg/gm UP/Cr ratio

Patients that have reached this milestone will be weaned off ACTHar Gel with or without Tacrolimus over the subsequent 14 days.

Sites will start the ACTHar Gel wean at 40 units and reduce over a 2 week taper period at the discretion of the principal investigator of each site.

Non-or Partial Responders: > 50% Reduction in UP/Cr ratio to minimum value of 2000 mg/gm:

Patients will follow the same weaning protocol as the complete responders described above.

- **Visit 9: ACTHar Washout Visit:**

14 Days Post End of Treatment (Visit 9) will be optional for patients traveling from long distances and will occur after the post treatment taper. The Study Staff will request that the patient visit a Nephrologist in the patient's home town if any adverse events of concern are reported.

- **Visits 10 -12: Follow-Up Visits-Months 15 (V10), 18(V11) & 9(V12):** We will be conducted in like manner to Randomization visit. Each patient will be get a complete physical exam. Standard blood and urine studies will be performed as well as plasma, serum and urine study sample collections.

- **Visit 13: Month 24 Visit: Secondary Endpoint Evaluation:**

Patients completing 104 weeks of study participation will be evaluated for the following:

1) Percentage of Complete Responder patients weaned off ACTHar gel and Tacrolimus that developed a relapse after 12 months of no therapy.

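### Urine for the biomarker endpoint gets proteinase inhibitor in the Visit 1 text but not in the baseline text, and month 12 has no handling rule, so matched samples are not secured

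*Protocol*

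**What the plan says.** Urine processing appears twice in the protocol's visit descriptions.

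- **Visit 1, Blood and Urine Study Samples:** "Each 10-ml sample of urine will be added to 100 ul of Thermo Scientific HALT proteinase inhibitor solution", followed by centrifugation, aliquoting and freezing.
- **Visit 3, Baseline - Blood and Urine Study Samples:** "A 10-ml sample of urine will be centrifuged at 3,000 rpm for 10 minutes at 4°C", followed by the same aliquoting and freezing. No inhibitor is mentioned.

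For Visits 5-7, and again for Visits 10-12, the text says "We will be conducted in like manner to Randomization visit". The Visit 8 (month 12) text has no such sentence and no study-sample paragraph. Its only urine instruction is "Patients will be asked to bring 2 first morning voids of urine", with the two values averaged for the UP/Cr endpoint. The Visit 13 text is also silent, as is the Visit 2 text.

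Secondary endpoint 4 is "To compare the change in urinary biomarkers (see below) at baseline and after 12 months of treatment". Specific Aim #3, which serves Hypothesis #3, uses the same two time points: "Levels will be measured at baseline prior to treatment and after 12 months". The schedule of assessments marks urinary biomarkers at both screening visits, baseline, months 3, 6 and 9, month 12, the follow-up visits and month 24, without saying how the samples are handled.

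**The concern.** The two paragraphs agree on urine volume, spin speed and time, temperature, aliquot and freezing. The inhibitor is the one substantive difference. The protocol therefore contradicts itself on a step it has chosen to specify. This is not a detail left to another document.

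The endpoint is a change between two samples. Such a change can be read as biology only if both samples were treated alike, or if the difference in treatment is known not to matter. The protocol secures neither. At month 12 a site could follow the Visit 1 wording, which speaks of each sample, or the Visit 3 wording, by analogy with the visits on either side.

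The biomarker baseline sample is also not named. Urine for biomarkers is collected at Visits 1, 2 and 3. For UP/Cr the protocol averages the pre-screening and randomization values. If that rule were carried over to the biomarkers, a single patient's baseline could mix urine with and without inhibitor.

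At stake is the reading of secondary endpoint 4, chiefly the within-arm change. A sample frozen without inhibitor cannot be given it afterwards.

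**Working it through.** The protocol states no figure to reproduce. The check is a comparison of the text by visit, then arithmetic for what a mismatch could do.

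**Handling by visit**

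| Visit | Biomarker urine scheduled | Handling in the text |
|---|---|---|
| 1 | yes | inhibitor, spin, freeze |
| 2 | yes | none given |
| 3 (baseline) | yes | spin, freeze; no inhibitor |
| 5-7 | yes | as Randomization visit |
| 8 (month 12) | yes | none given |
| 10-12 | yes | as Randomization visit |
| 13 (month 24) | yes | none given |

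Of the two endpoint samples, one has a procedure that conflicts with the Visit 1 text and the other has no procedure.

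**Dilution.** Adding 0.1 ml to 10 ml gives 10/10.1 = 0.990, a loss of about 1%. Any material artefact would have to come from protein loss.

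**Artefact in within-patient relative change, with no true change.** Let r be recovery without inhibitor relative to recovery with it. The documents give no value, so r = 0.7 to 1.0 is an assumption that includes no loss at all.

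| Handling | Formula | r = 1.0 | r = 0.9 | r = 0.7 |
|---|---|---|---|---|
| Same at both visits | r/r - 1, or 1/1 - 1 | 0% | 0% | 0% |
| Inhibitor at month 12 only | 1/r - 1 | 0% | +11% | +43% |
| Inhibitor at baseline only | r - 1 | 0% | -10% | -30% |
| Baseline is the mean of one Visit 1 and one Visit 3 sample; month 12 without inhibitor | 2r/(1 + r) - 1 | 0% | -5% | -18% |
| Same mixed baseline; month 12 with inhibitor | 2/(1 + r) - 1 | 0% | +5% | +18% |

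For the last two rows at r = 0.7: 1.4/1.7 - 1 = -0.18 and 2/1.7 - 1 = +0.18.

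**Between-arm comparison.** Let c1 and c2 be the true month-12 to baseline ratios in the two arms. If every patient's ratio is multiplied by the same artefact k, the comparison is (k × c2)/(k × c1) = c2/c1, and the artefact cancels. If k differs among sites, it does not cancel patient by patient and adds variance. With 34 patients over 7 to 10 sites there are 34/10 = 3.4 to 34/7 = 4.9 patients per site, so a chance imbalance of sites between arms of 17 is plausible.

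**The case against.** The strongest reply is that no text prescribes different handling for the two endpoint samples. Two coherent readings both give matched handling. In one, Visit 8 lies between visits that copy the Randomization visit and shares their schedule rows, so it follows the same procedure and neither endpoint sample has inhibitor. In the other, the Visit 1 wording about each sample is a general rule, the baseline paragraph simply omits the step, and both samples have inhibitor. Bias needs a mixed reading. This stands: the mismatch is a possibility that the protocol leaves open, not an instruction it gives. It does not remove the contradiction, because the protocol does not choose between the two readings and does not name the baseline sample.

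It can also be said that both paragraphs spin at 4°C and freeze at -80°C, that the schedule lists these markers under an exploratory heading although the endpoint list calls them secondary, and that UP/Cr, eGFR and response rates do not depend on this step. All of this is correct and limits the scope.

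A reader might infer that handling alone could hide or create an effect as large as the 40% the trial is sized for. The documents do not support that. The 40% is a between-arm difference in UP/Cr, a different analyte, whereas the handling artefact is a within-arm shift that largely cancels between arms when it is common to both. Choosing an assumed loss of 40% to match a 40% effect would also be circular. Nor does the protocol say that the inhibitor is necessary; it prescribes it in the Visit 1 paragraph and gives no rationale.

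**Conclusion.** The point holds as an internal contradiction with a conditional consequence. The protocol specifies two urine procedures for one set of assays and has no rule for month 12, so it does not secure like-for-like samples at the two time points of secondary endpoint 4 and Specific Aim #3.

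The size is unknown. It is zero if the two samples are handled alike and recovery is constant. Under the assumed recovery range it reaches at most +43% or -30% in the within-arm change. Hypothesis #3 is a between-arm comparison and is exposed mainly through extra noise if handling varies among sites; the documents neither state nor exclude such variation. The primary endpoint is untouched. The correction is worth making because it is cheap before collection and cannot be made after freezing.

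**What to change.** 1. Replace the Visit 1 and Visit 3 urine paragraphs with one procedure, including the Visit 1 inhibitor step, and state that it applies to every biomarker collection, naming Visits 3, 8 and 13.
2. Name the pre-treatment sample, or the rule for combining samples, that defines the biomarker baseline.
3. Record inhibitor use with each sample, flag urine already stored without it, and compute changes from like-handled pairs.

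The cost is one corrected paragraph, one field on the sample record and 100 ul of reagent per 10-ml sample. Sample size and visits do not change. Restricting to like-handled pairs may lose some patients from the biomarker analysis if samples have already been stored under both procedures.

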Inclusion Criteria	
Histologic Inclusion Criteria
 
Histologic Criteria: All patients with a diagnosis of The Fibrillary GN will be classified according to the Nasr nomenclature:
 
1) Renal biopsy demonstrating DNA-JB9 Positive staining within 3 years of study randomization2) Mesangial expansion with/without glomerular sclerosis3) Membranous changes with or without diffuse sclerosis4) Crescents or endocapillary proliferation5) Level of interstitial fibrosis 
Note: Patients with > 50% interstitial fibrosis will not be eligible for study participation
 
Note: Patients with monoclonal staining of fibrillary fibers will not be eligible for study participation
 
Inclusion Criteria:
 
1) Male/Female age \geq 182) Biopsy proven Fibrillary GN within 3 years of study randomization3) Stable Maximum RAAS inhibition X 4 weeks prior to randomization 
Note: Maximum RAAS inhibition will be left to the discretion of the site PI
 
4) eGFR > 25 mls/min calculate by the CKD-EPI formula5) UP/Cr ratio \geq 2000 mg/gm

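### No chemistry panel in either arm, and no tacrolimus trough in Group 2, is scheduled between baseline and month 3 (weeks 11-15 of 52)

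*Protocol*

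**What the plan says.** **Dosing.** Group 2 starts tacrolimus at 1.0 mg twice daily. The Study Population entry has it "titrated to trough Tacrolimus levels between 4-6 ng/ml", and Drug Dosing repeats the target as "titrating to a trough level of 4-6 ng/ml for 52 weeks".

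**Who may enter.** The Inclusion Criteria require "eGFR > 25 mls/min calculate by the CKD-EPI formula" and "Stable Maximum RAAS inhibition X 4 weeks prior to randomization". Both apply to both arms.

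**Visit 3 (baseline).** Routine blood and urine tests are done, and the schedule marks study drug from this visit.

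**Visit 4 (day 14).** The text reads "14 Days Post Randomization (Visit 4) will be optional for patients traveling from long distances". It names no laboratory test. For adverse events it adds "Would request that patient visit nephrologist in home town if any adverse events of concern are reported".

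**Visits 5-7 (months 3, 6 and 9).** The text orders laboratory work: "Standard blood and urine studies will be performed as well as plasma, serum and urine study sample collections". It then adds "Tacrolimus Trough Levels will be drawn for those patients randomized to the Tacrolimus arm".

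**Hyperkalemia section.** A potassium above 5.5 meq/L starts a five-step sequence of interventions. The section is not limited to Group 2, although two of its steps concern tacrolimus dose.

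**The concern.** A dose that is titrated to a blood level needs a measured level, and a rule triggered by potassium needs a measured potassium. The schedule supplies neither during roughly the first quarter of treatment. The protocol itself foresees hyperkalemia, and its last two steps reduce and then stop tacrolimus. It also admits patients with limited kidney function on maximum RAAS inhibition.

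A raised potassium without symptoms, or a trough outside 4-6 ng/ml, could go unseen until month 3 unless a site chose to test earlier. The home-town nephrologist request would not catch it, because it depends on a reported adverse event and names no test. What is at stake is patient safety in both arms and early tacrolimus dosing in Group 2.

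**Working it through.** The protocol gives no figure to reproduce. The check is a reading of the schedule of assessments against the visit text, followed by calendar arithmetic.

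**Step 1. Schedule of assessments.**

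| Row | V1 | V2 | V3 | V4 | V5-7 | V8 | V9 | V10-12 | V13 |
|---|---|---|---|---|---|---|---|---|---|
| CMP | X | X | X | – | X | X | – | X | X |
| Tacrolimus trough | – | – | – | – | X | X | – | – | – |
| Limited H&P | – | X | – | X | X | X | X | X | – |
| AE/SAE | – | – | X | X | X | X | X | X | X |

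CBC, UA and UP/Cr follow the CMP pattern. Visit 4 is marked for limited H&P, blood pressure, ACE/ARB stability and AE/SAE. Its column therefore survived extraction, and the blank laboratory cells are not a lost column. The visit text, read separately, also orders no test at Visit 4.

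**Step 2. Does anything else fill the gap?** The study-sample text calls for 5 ml of blood at every visit, but those aliquots are frozen for later analysis. They give no result on which a site could act.

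**Step 3. Timing as written.** Month 3 = 52/4 = week 13, and the window for Visits 5-7 is ± 2 weeks.

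- Earliest: 13 − 2 = week 11; 11/52 = 21% of the course.
- Latest: 13 + 2 = week 15; 15/52 = 29% of the course.

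**Step 4. Timing if the tests were done at Visit 4.** Day 14 = week 2, with a window of ± 1 week.

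- Earliest: week 1; 1/52 = 2%.
- Latest: week 3; 3/52 = 6%.
- Nominal gain: 13 − 2 = 11 weeks.
- Range of gain: 11 − 3 = 8 weeks to 15 − 1 = 14 weeks.

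**Step 5. Sensitivity.** If month 3 is read as 12 weeks, the window is weeks 10-14 and the nominal gain is 12 − 2 = 10 weeks. The conclusion does not change.

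**Step 6. What remains scheduled.** Three troughs (months 3, 6 and 9) precede the month 12 endpoint visit, and a fourth is drawn at that visit.

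**The case against.** The strongest reply is that a schedule sets a minimum. An instruction to titrate to a level implies drawing levels as needed, unscheduled tests are not forbidden, and the protocol openly leaves much metabolic management to the site investigator. This stands in part: it would be wrong to infer that Group 2 patients are unmonitored for three months. The supportable statement is only that early tests are neither required nor timed, so they may differ across the 7-10 sites.

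A second reply is that the documents give no rate of hyperkalemia or of off-target troughs, and no benchmark that makes month 3 too late. That also stands, and it limits the weight of the point.

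Third, a reader might want to confine the extra tests to Group 2. The documents do not support that for chemistry. CMP is blank at Visit 4 for everyone, and the eGFR and RAAS criteria and the potassium rule apply to both arms. The trial is open-label and compares adverse event frequencies with a Fisher exact test. An additional early panel in one arm would find more laboratory abnormalities in that arm alone.

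Fourth, a reader might infer that the potassium sequence is itself defective, because its later steps depend on persisting hyperkalemia and no recheck time is stated. That does not follow. Those later steps are permissive, and once a high value is known the timing of a repeat is ordinary clinical judgement. The same holds for repeat troughs after a dose change.

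**Conclusion.** The point holds as a scheduling gap. In the visible text and the schedule, the first on-treatment CMP (both arms) and the first tacrolimus trough (Group 2) come at weeks 11-15, after 21-29% of the 52-week course. This sits poorly with a titration target of 4-6 ng/ml and with the entry criteria for eGFR and RAAS inhibition.

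The conclusion rests on two assumptions: that no early laboratory rule stands in text missing from the copy reviewed, and that month 3 means about week 13.

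A reader might go further and infer that the primary UP/Cr comparison is compromised by poor early tacrolimus exposure. The documents do not support this. They give no rate of off-target troughs, and three scheduled troughs precede the month 12 evaluation. The gap concerns safety monitoring and dosing and is cheap to close.

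**What to change.** In the schedule of assessments and in the Visit 4 text, add for day 14 ± 1 week:

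- a CMP in **both arms**, so that laboratory safety ascertainment stays equal;
- a tacrolimus trough in **Group 2**;
- a local laboratory draw for both tests where a long-distance patient is excused from the visit. Without this, the patients who skip the visit would still have no result before month 3.

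The cost is one extra CMP in 34 patients and one extra trough in 17, plus the arrangements for local draws. Local laboratories may use different assays, so some between-laboratory variation should be accepted when the early results are read. Sample size, power and endpoints do not change.
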